Unique Protocol ID: JCHP-2

Brief Title: Omega-3 Supplementation to Both Parent and Adolescent

Official Title: Omega-3 Supplementation to Both Parent and Adolescent to Reduce Behavior Problems

Document Date: May 16, 2018

Experimental Design and Methods

This section provides the design and method of the overarching study within which the three aims will be tested. We also briefly specify further programmatic goals of this line of study, and also how the specific expertise of the research team will help ensure feasibility. As with the pilot study, methodology and ultimately reporting of results will follow CONSORT 2010 guidelines (Moher et al., 2010).

Design Overview

The study design will consist of a stratified, double-blind, placebo-controlled, factorial, randomized controlled trial of children and their caregivers in a community sample in Mauritius. This closely follows the design of the pilot study (Raine et al. 2015). Unlike the pilot study however, it will utilize a 2x2 factorial design, in which children *and* their parents will be randomly assigned to either omega-3 supplementation (treatment condition) or a placebo (control condition), and will have an extended follow-up at 18 months. This results in 4 groups: (1) child and caregiver both receiving omega-3, (2) child receives omega-3, caregiver receives placebo, (3) caregiver receives omega-3, child receives placebo, (4) both parent and child receive placebo. Assessments will take place at 0 months (baseline), 6 months (end of supplementation), 12 months (6 months post-treatment), and 18 months (12 months post-treatment).

Background To The Sample and the Mauritius Child Health Project

Adolescents and caregivers will be drawn from the Mauritius Child Health Study, a multi-generational study involving three generations of subjects. Details of these three generations are provided in a cohort profile (Raine et al. 2010). Originally set up by [name] (Consultant), this longitudinal study covers early child health and development and the identification of early risk factors (including nutrition) for later psychopathology, as well as early primary prevention. Early factors that shape later cognitive functioning have also been a focus. Given the pilot findings and longitudinal data on the parents, it provides a unique platform on which to build.

Participants, Potential Attrition, and Strategies to Deal with Attrition

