Aims 1 and 2 (Primary Outcome). These hypotheses will be addressed using adolescent and caregiver externalizing responses gathered at baseline and at 6, 12, and 18 month follow-ups. Responses for the adolescent will be analyzed separately from responses for the caregiver. For each separate set of responses, linear mixed effects models (Molenberghs & Verbeke, 2005) will be used to describe both the pattern of response and the within-subject covariance structure across time points. Primary analyses will not include baseline covariates, as the randomization will balance the treatment groups and eliminate selection bias. To enhance power by controlling for variability in response (Kahan et al., 2014), a small set of baseline covariates (e.g. gender, age, ethnicity) will be included in supplementary analyses.

The response may be transformed (e.g. log transformation) to reduce levels of skewness in the response to acceptable levels, as assessed by examination of residuals. Models will include binary indicators for adolescent group (omega-3 vs placebo), caregiver group (omega-3 vs placebo), and time (four level factor for times 0, 6, 12, and 18), and group by time interaction terms, as fixed effects. Time is modeled as a discrete factor to accommodate the patterns observed in our prior study (see Figure under Preliminary Data) where the omega-3 adolescent groups are similar at baseline and 6 months, and separate at 12 months. Covariance structure models (e.g. random effects, autocorrelated residuals) will be compared using information criteria in models containing all main effects and interactions of interest. Once the covariance structure has been chosen, the fixed effects will be assessed for significance using likelihood ratio tests.

Parameter estimates, standard errors, and 95% confidence intervals will be reported. In the case of a multiple degree of freedom test (e.g. group by time interaction, with 3 df), single-df contrasts will be estimated and reported, to explain the nature of the interaction.

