For the adolescent, Hypothesis 1a will be addressed using a child group by time interaction term (time trends for omega-3 and placebo group need not be parallel), or a child group main effect if the interaction term is non-significant (parallel time trends). Similar models will address the corresponding Hypothesis 1b for the caregiver responses. For both the adolescent and caregiver responses, Hypothesis 2a will be tested by an adolescent group by caregiver group by time interaction, or by an adolescent by caregiver interaction if the four adolescent by caregiver group trends are parallel.

Aim 3 (Secondary Outcome). Working hypothesis 3a (change in neurocognitive and academic factors) will be tested using the same mixed effects models as outlined above in aims 1 and 2. Working hypothesis 3b (mediation), whether improvement in neurocognitive variables (e.g. impulse control) or academic WRAT scores partly account for the treatment effect on child behavior will be assessed using mediation analyses. Based on the prior study (Raine et al, 2015), effects of supplementation should emerge by the 12-month time point. Analyses will test whether changes in risk factors between baseline and the 6 month point mediate the 12-

month treatment effect. These analyses will be conducted using the PROCESS SPSS macro (Hayes, 2012), which will also be used to assess moderated mediation (e.g. neurocognitive measures mediate outcomes more strongly in younger adolescents). To test significance of the indirect effects (i.e. mediation), bias-corrected confidence intervals for the indirect effects will be generated using 10,000 bootstrap samples. To assess extent of mediation, the reduction in variance explained in treatment outcome by the intervention after controlling for improved parental behavior (the mediator) will be calculated in a two-step regression. Equivalent analyses will be performed for the other neurocognitive variables.

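### The fallback test for Hypotheses 1a, 1b and 2a averages in the pre-treatment visit, so it understates any real effect

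*Combined protocol and SAP*

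**What the plan says.** Design Overview: "Assessments will take place at 0 months (baseline), 6 months (end of supplementation"), then 12 months, and the trial "will have an extended follow-up at 18 months". Month 0 is therefore before treatment.

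Statistical Methods, Aims 1 and 2: month 0 is part of the response. The fixed effects are the two group indicators, "time (four level factor for times 0, 6, 12, and 18), and group by time interaction terms, as fixed effects". Nothing sets the group means equal at month 0. The primary model has no baseline covariates. Supplementary analyses add a few, with gender, age and ethnicity as examples.

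Decision rules in the same section:
- Hypothesis 1a: the child group by time interaction, "or a child group main effect if the interaction term is non-significant (parallel time trends").
- Hypothesis 1b: "Similar models will address the corresponding Hypothesis 1b for the caregiver responses".
- Hypothesis 2a: the three-way term, "or by an adolescent by caregiver interaction if the four adolescent by caregiver group trends are parallel".

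No sentence limits any fallback to post-baseline visits, and no significance level is given for either step.

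On the expected pattern, the section describes pilot data "where the omega-3 adolescent groups are similar at baseline and 6 months, and separate at 12 months". Aim 3 says that "effects of supplementation should emerge by the 12-month time point".

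**The concern.** Once the interaction is dropped, the group main effect is an average difference over all four visits, one of which precedes treatment. Its premise is a constant difference from month 0 onward. In a randomized trial the expected difference at month 0 is zero, so a constant difference is zero throughout. Any real effect makes the trends non-parallel, as the plan's own pilot description shows. A non-significant 3-df test does not establish parallelism; it may simply have missed the effect.

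A real effect missed at step one therefore goes to a step that understates it, and that estimate becomes the answer to a primary hypothesis.

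Two smaller points concern efficiency, not bias. With free month 0 means, each group by time contrast is a change-score comparison, which is less precise than a baseline-adjusted one. The urn variables are also left out of the primary model. The supplementary covariate analyses cure neither the month 0 averaging nor the free baseline means.

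**Working it through.** The plan states no power calculation, so there is no figure to reproduce.

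**Inputs.** From the documents: 400 pairs, 8% pilot attrition, visits at months 0, 6, 12 and 18, and a 3-df interaction. Completers: 400 × 0.92 = 368. Assumed: SD 1, effect d = 0.2 SD, within-person correlation ρ = 0.6 under CS (0.4, 0.8 and AR(1) also tried), two-sided 5% tests, complete data and a normal approximation. Three effect patterns are used: all follow-ups; months 12 and 18; month 12 only. The documents support an effect by month 12; its persistence to month 18 is an assumption.

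**1. Dilution.** Under CS the main effect weights each visit by 1/4.

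| Pattern | Fallback estimate | Mean of months 6, 12, 18 |
|---|---|---|
| All follow-ups | 3/4 × 0.2 = 0.15 | 0.20 |
| Months 12 and 18 | 2/4 × 0.2 = 0.10 | 0.133 |
| Month 12 only | 1/4 × 0.2 = 0.05 | 0.067 |

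Under AR(1) with ρ = 0.6 the month 0 weight rises to 0.357, and the first row becomes 0.643 × 0.2 = 0.129 SD.

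**2. Precision.** The group difference at one visit has variance V = 4/368 = 0.01087.
- Fallback: V(1+3ρ)/4 = 0.01087 × 0.70 = 0.00761, SE 0.087.
- Baseline-adjusted mean of months 6, 12, 18: V[(1+2ρ)/3 − ρ²] = 0.01087 × 0.3733 = 0.00406, SE 0.064.

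For all follow-ups, z is 0.15/0.087 = 1.72 against 0.20/0.064 = 3.14. As single steps the powers are about 40% v 88%; for the other patterns, 21% v 55% and 9% v 18%.

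**3. Power where the fallback is used** (simulation of the group-difference vector, 400,000 draws per case, ρ = 0.6).

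| Pattern | Fallback reached | Fallback power there | Adjusted average, same trials | Gain over all trials |
|---|---|---|---|---|
| All follow-ups | 42% | 40% | 74% | about 14 points |
| Months 12 and 18 | 28% | 21% | 31% | about 3 points |
| Month 12 only | 42% | 9% | 9% | none |

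The last column is the share reaching the fallback times the power difference. Under the null, the adjusted average rejects in 3.8% of these trials and the fallback in 5.0%, so the gain is not bought with false positives. In pattern order, fallback v adjusted average is 49 v 73, 25 v 34 and 10 v 11% at ρ = 0.4, and 34 v 84, 18 v 30 and 8 v 7% at ρ = 0.8.

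**4. Interaction test.** Under CS the noncentralities are:
- free month 0 means: [Σd² − (Σd)²/4] / [V(1−ρ)];
- equal month 0 means: [Σd² − ρ(Σd)²/(1+3ρ)] / [V(1−ρ)].

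With V(1−ρ) = 0.00435, all follow-ups give 0.03/0.00435 = 6.90 (free) and 0.04286/0.00435 = 9.86 (equal). The difference, 2.96, is exactly the fallback's own noncentrality (0.15²/0.00761). The 3-df powers, free v equal, are 58 v 75%, 72 v 78% and 58 v 60.5%. For a single visit the variance ratio, equal to free, is (1+ρ)/2 = 0.80.

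**5. Whole two-step rule.** The model-based main effect is independent of the change contrasts, so power is 1 − (1−p₁)(1−p₂). For all follow-ups this is 1 − 0.417 × 0.595 = 75%; for the other patterns, 78% and 62%. Type I error is 1 − 0.95² = 9.75%. Holding it at 5% needs 1 − √0.95 = 2.53% per step, and power falls to 63 / 68 / 50%. One 3-df test at 5% with equal month 0 means has 75 / 78 / 60.5%.

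**6. Hypothesis 2a.** With 92 completers per cell the variance is 4/92 = 16/368, so the SE doubles. The dilution fractions are unchanged, and the powers above apply to a 0.4 SD difference of differences.

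**7. Urn variables.** If these explain 10–20% of variance, an assumed four-arm urn gives the unadjusted fallback a true level of about 4.6–3.8% at ρ = 0.6. This is mildly conservative. It costs nothing in the interaction if the covariate effects are constant over time.

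**The case against.** The interaction is the main test, and larger effects seldom reach the fallback: at 0.3 SD in months 12 and 18 (CS, 0.6) the interaction has 97.9% power, against 99.0% with equal month 0 means. The largest losses come from an effect at every follow-up, which the pilot description does not support. For later effects the gain over all trials is about 3 points or nothing, and part of the dilution then comes from month 6. The two-step rule as written also has about the same power as the proposed single test. Free baseline means are a standard, unbiased choice. The plan promises single-df contrasts, so undiluted visit differences might be reported as well.

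Much of this stands as a limit on size. The equal power, however, is reached only with nearly twice the type I error. At a matched 5% the single test leads by 3 to 12 points over CS and AR(1) at 0.4 to 0.8. A good part of that lead is the cost of splitting alpha: for month 12 only at CS 0.6, just over 2 of the 10.5 points come from equating month 0 means. The single-df contrasts are offered to explain an interaction, so they do not clearly cover the case where it is non-significant. None of the objections supplies a reason to average in a visit at which no effect can exist.

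**Conclusion.** The concern holds. As written, the fallback for Hypotheses 1a, 1b and 2a includes month 0, and its parallel-trends premise is compatible only with no treatment effect. The 1/4 weight on month 0 under CS does not depend on effect size or correlation; under AR(1) the weight is larger.

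The practical loss depends on assumed inputs. At 0.2 SD and CS 0.6 it is large for an effect at all follow-ups, modest for months 12 and 18, and nil in power for month 12 only, although the estimate is still diluted. It matters most for small effects and for Hypothesis 2a, whose variance is four times larger. The 9.75% error rate assumes 5% at each step. The free-baseline and urn points are efficiency losses only and can be small; for a month 12 effect alone, equating baseline means adds 0 to 3 points to the interaction test. The plan should be changed, but the interaction test itself is not invalid.

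**What to change.** 1. Define any overall group effect, and the adolescent by caregiver effect for Hypothesis 2a, over months 6, 12 and 18 only, adjusted for baseline externalizing.
2. Make primary either a model with month 0 means constrained equal across the randomized groups, or one with months 6, 12 and 18 as responses and baseline externalizing by time as covariate.
3. Test each hypothesis with that model's 3-df test. It also detects a constant post-baseline shift, so no fallback is needed. If two steps are kept, state their levels and control the joint type I error.
4. Include the urn variables actually used in allocation (parental externalizing only if it was used).
5. Keep the unadjusted model as a sensitivity analysis.

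The cost is SAP wording. Baseline externalizing and the allocation variables are already collected.

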Participants will be randomized into four groups using urn randomization, a covariate adaptive randomization method (Wei & Lachin, 1988). Adaptive randomization is employed because it protects the study from bias while promoting study objectives, it improves power over standard designs, and it balances assignment of treatment across covariates in a way superior to traditional stratification (Rosenberger et al., 2012). We aim to achieve balanced groups on three main child covariates: age, gender, and ethnicity. An advantage of the Mauritius cohort is that we have data on the parents' externalizing behavior over the life-course (Raine et al. 2010) which we could add as a fourth covariate to further ensure that groups are balanced.

Omega-3 Intervention

Omega-3 supplementation. As in the pilot study, this consists of a 200 ml drink. The base drink in both treatment and placebo conditions consists of fruit juice containing vitamin D (0.85 micrograms) and antioxidants (ferric reducing ability of plasma value of 0.71 mmol/100g). For the treatment condition only, 1660 mg of omega-3 (550 mg of DHA, 550 mg of EPA, 560 mg of alpha-linolenic acid) is added to the base drink. Placebo drinks are matched exactly with the fish-oil drink in terms of size, appearance, and flavor. Caregiver and child drinks are differentially color-coded.

This drink is chosen because: (i) it contains a higher dosage of omega-3 than standard capsules in a small liquid quantity (60.6% of a standard can of cola) suitable for child / adolescent consumption, (ii) the fruit-flavored drink may be better tolerated and result in higher compliance with children than fish-oil capsules.

Treatment duration and administration. As in the pilot study, treatment duration will be six months. It was chosen because prior studies have usually been 2 - 4 months (Sinn et al., 2010), and a longer duration may be more effective in producing longer-term behavioral change. The drink will be administered by the parents to their children at any time each day.

Primary Outcome Measures

The pre-defined primary outcome measures are externalizing behavior problems. Secondary outcomes included internalizing behavior problems and neurocognitive / academic mediators. We include additional *secondary* measures of reactive-proactive aggressive behavior and callous-unemotional traits to replicate the pilot findings and explore antisocial subtypes (the pilot data showed stronger effects for reactive aggression).

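### Four primary hypothesis-level tests have no stated alpha, lead hypothesis, order or adjustment, and H2a has no one-or-both rule; at an assumed 5% each, a null trial gives a positive primary result at least about 16–18% of the time

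*Combined protocol and SAP*

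**What the plan says.** The combined protocol and SAP defines the primary outcome as a construct and not as a particular test: "The pre-defined primary outcome measures are externalizing behavior problems" (Primary Outcome Measures). Statistical Methods then places two aims under the primary label: "Aims 1 and 2 (Primary Outcome). These hypotheses will be addressed using adolescent and caregiver externalizing responses gathered at baseline". Two people's scores are involved, and "Responses for the adolescent will be analyzed separately from responses for the caregiver".

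The tests under that label are:

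- **H1a, adolescent score:** the child-group-by-time interaction, "or a child group main effect if the interaction term is non-significant (parallel time trends").
- **H1b, caregiver score:** "Similar models will address the corresponding Hypothesis 1b for the caregiver responses".
- **H2a, both scores:** "For both the adolescent and caregiver responses, Hypothesis 2a will be tested by an adolescent group by caregiver group by time interaction". The fallback drops time and keeps the two-way term: "or by an adolescent by caregiver interaction if the four adolescent by caregiver group trends are parallel".

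No significance level is given. The nearest indication is "Parameter estimates, standard errors, and 95% confidence intervals will be reported". No section names a deciding hypothesis, an order of testing across hypotheses, an alpha split or a multiplicity adjustment. Moderator Analyses also speaks of the primary hypotheses in the plural. The document refers to H1a, H1b and H2a by number; their full wording does not appear in it.

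**The concern.** Four results can each be called a primary result, and the plan does not say which of them makes the trial positive. If only H1b were significant, or only H2a on the caregiver score, a reader could not tell from the plan whether the trial had met its primary objective.

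H2a is the sharpest case. It is one hypothesis with two chances of being declared, because the plan does not say whether significance on either response is enough or both are needed. Even if every single test holds its level, the set of primary claims does not.

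The only ordering in the plan lies inside each hypothesis, from the time interaction down to a lower-order term. That gives each hypothesis a second chance of significance and controls nothing across hypotheses.

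**Working it through.** **The plan's own figures.** There is no alpha, power or error rate to reproduce. The sample size is cell arithmetic: 4 × 100 = 400 pairs, and 2 × 400 = 800 people.

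**Inputs.**
- Hypothesis-level tests: four (Statistical Methods, Aims 1 and 2).
- Equal cells of 100 pairs (Participants section).
- Time interactions on 3 df (Statistical Methods).
- Assumed: two-sided 5% per test, suggested only by the 95% intervals.
- Assumed: H1b tests the caregiver's drink on the caregiver's score, inferred from the statement that it corresponds to H1a.
- Assumed: a child–caregiver outcome correlation r from 0 to 0.9, since the document gives none.

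**Which tests are correlated.** With equal cells, code the child's drink as (1, 1, −1, −1) and the caregiver's drink as (1, −1, 1, −1). Their product sums to 1 − 1 − 1 + 1 = 0. The interaction (1, −1, −1, 1) is orthogonal to both in the same way. H1a and H1b are therefore independent under the null even when the two people's scores are correlated. The two H2a tests use the same contrast, so they share the correlation r.

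**One test per hypothesis, independent.** 1 − 0.95⁴ = 18.5%.

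**The rule as written.** If the fallback is taken whenever the interaction is non-significant, and the two steps are independent, each hypothesis has an error rate of 1 − 0.95² = 9.75%. The family has 1 − 0.95⁸ = 33.7%.

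**With correlated outcomes** (null simulation, one million draws of the 3-df and 1-df statistics):

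| r | One test each | Two-step rule |
|---|---|---|
| 0 | 18.6% | 33.7% |
| 0.3 | 18.4% | 33.3% |
| 0.5 | 18.0% | 32.7% |
| 0.7 | 17.5% | 31.7% |
| 0.9 | 16.2% | 29.7% |

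**H2a alone, declared on either response, one 3-df test each:** 9.7%, 9.2% and 8.5% at r = 0, 0.5 and 0.7.

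**Finite-sample check.** Simulated null trials (12,000 at each of r = 0, 0.3 and 0.5) used 4 × 100 pairs, four visits and likelihood ratio tests under compound symmetry. They gave 18.4–19.6% with one test each and 33.0–35.0% with the two-step rule.

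**Sensitivity.**
- If H1b used the child's drink instead, the one-test figures at r = 0.3, 0.5, 0.7 and 0.9 would be 18.2%, 17.5%, 16.2% and 13.8%. The lowest two-step figure would be 25.5%, at r = 0.9.
- At 1% per test, the family rate would be 1 − 0.99⁴ = 3.9% with one test each and 1 − 0.99⁸ = 7.7% with the two-step rule.

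**The case against.** The strongest reply is that this is a 2×2 factorial trial. H1a and H1b concern different people's scores and, as inferred, different randomised drinks. Testing each such question at its own 5% is a defensible position. That stands, and a reader should not infer that the two must share one alpha. But the plan does not take this position explicitly, and the position does not help H2a, which is a single hypothesis with two chances.

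A reader might infer three further things that the document does not support:

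- **That 18% is this trial's false-positive rate.** It is the rate for a simpler plan with one test per hypothesis. The written rule gives about 30–34%. Both figures depend on an alpha that the plan never states.
- **That the plan lets any one of the four results make the trial positive.** It says no such thing. It is silent, and the silence is the defect.
- **That unfavourable results could be left out.** The plan commits to reporting estimates, standard errors and 95% intervals, and to CONSORT 2010. All four results should therefore be visible, although visibility does not control the error of a primary claim.

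It can also be said that the hypotheses' full wording is not in the document, so a lead hypothesis may be named in text that is not here. That is a fair limit. Even so, the Statistical Methods section, where an analyst would look for the rule, gives none.

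**Conclusion.** The point holds. The firmest part needs no arithmetic: no result is named as deciding the trial, and H2a has no one-or-both rule.

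The size rests on an assumed two-sided 5%. With one test per hypothesis, the chance of at least one false primary result is about 16–18% for outcome correlations from 0.3 to 0.9, and 18.5% under independence. This is a floor for the plan as written at that alpha, because the two-step rule takes the family to about 30–34%. H2a on either response is about 9%. The 16–18% range also assumes that H1b uses the caregiver's drink; on the other reading only a very high correlation (0.9) takes it lower, to 13.8%.

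The change is worth making because it is cheap and settles what counts as a positive trial. The point does not show that H1a, taken alone with a single test, would be invalid.

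**What to change.** In Statistical Methods, Aims 1 and 2:

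1. State a two-sided alpha of 5%.
2. Give each hypothesis one prespecified test in place of the interaction-then-lower-order rule. The steps below depend on this: a sequence led by a two-step H1a would still run at about 9.75%.
3. Name one lead hypothesis that decides the trial, for example H1a on the adolescent score.
4. Name one response as decisive for H2a and the other as supportive.
5. Test the remaining hypotheses in a prespecified fixed order. If the sponsor wants them co-primary, use Holm or a Bonferroni split instead. For four tests the split is 0.05/4 = 0.0125 each, with a family rate of 1 − 0.9875⁴ = 4.9% under independence. If step 4 leaves three tests, it is 0.05/3 = 0.0167 each. If the two-step rule were kept after all, eight tests would need 0.05/8 = 0.00625 each.
6. If H1a and H1b are meant as separate factorial questions, each at 5%, say so and do not present them as one primary claim.

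The cost is a few sentences of wording. Under a fixed order the lead hypothesis keeps the full 5%, but later hypotheses cannot be claimed as confirmed if an earlier one fails. That matters for H2a, the question the factorial design makes possible, so the sponsor should choose the order deliberately. Under a split every test loses some power. In either case all estimates and 95% intervals are still reported.

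### The mediation models for hypothesis 3b name no covariates; without baseline values and month-6 behavior, a month-6 test score can look like a mediator when it is not

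*Combined protocol and SAP*

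**What the plan says.** Statistical Methods, Aim 3 (Secondary Outcome), asks whether improvement in neurocognitive or WRAT scores may "partly account for the treatment effect on child behavior will be assessed using mediation analyses". On timing it expects that "effects of supplementation should emerge by the 12-month time point", and so "Analyses will test whether changes in risk factors between baseline and the 6 month point mediate" the 12-month effect. On method, "These analyses will be conducted using the PROCESS SPSS macro", and "bias-corrected confidence intervals for the indirect effects will be generated using 10,000 bootstrap samples".

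No covariate is listed for these regressions: not the baseline score, not baseline behavior, not behavior at 6 months. Nor does the section say whether the outcome is the 12-month score or the change from baseline.

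The behavior data exist. Under Aims 1 and 2, "These hypotheses will be addressed using adolescent and caregiver externalizing responses gathered at baseline and at 6, 12, and 18 month follow-ups". That section leaves covariates out of its primary analyses because of randomization, and gives gender, age and ethnicity as examples for supplementary ones. It does not mention the mediation models.

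A separate matter in the Aim 3 paragraph is that the variance-explained step is done "after controlling for improved parental behavior (the mediator) will be calculated in a two-step regression", whereas hypothesis 3b names neurocognitive and academic scores. That needs reconciling but does not change the present point.

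**The concern.** No child is randomized to a test score, so the step from score to later behavior is observational. Two things can distort it.

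- **Baseline.** Raw change in a score depends on where the score started. If score and behavior correlate at baseline, raw change correlates with later behavior for that reason alone.
- **Months 0-6.** An adolescent whose behavior worsens during supplementation may test worse at month 6 and will tend to behave worse at month 12. The score then predicts later behavior without causing it. Baseline values cannot remove this, because the disturbance arises after baseline.

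If the drink also moves the score, the product of the two paths is non-zero and reads as mediation. At stake is the trial's mechanistic claim. The lag from 6 to 12 months is meant to show cognition changing first and behavior later. A model without month-6 behavior cannot separate that from the reverse order.

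**Working it through.** **Figures from the documents.** 400 pairs and 8% pilot attrition (Participants section) give 400 × 0.92 = 368 children at 12 months. The plan states no effect size, correlation or power for the mediation test, so there is no figure to reproduce.

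**Assumptions.** M is the test score and Y is externalizing, each with SD about 1 at baseline. X is child group, split 1:1.
- Y6 = 0.6·Y0 + e6, with var(e6) = 1 − 0.36 = 0.64
- M6 = 0.3·X + 0.6·M0 − g·e6 + u, with var(u) = 0.75² = 0.5625
- Y12 = 0.6·Y6 − 0.3·X + error, with error variance 0.64
- g = 0.1, 0.2 or 0.3; r0 is the baseline correlation of M0 and Y0

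The score has no effect on behavior, so any mediation found is false.

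**Baseline score and behavior in the model.** What remains of the score is −g·e6 + u, and what remains of Y12 is 0.6·e6 + error. So

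b = −0.6·g·0.64 / (0.64·g² + 0.5625)

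| g | score-behavior partial correlation at month 6 | b | indirect effect, 0.3·b |
|---|---|---|---|
| 0.1 | −0.11 | −0.0384/0.5689 = −0.067 | −0.020 |
| 0.2 | −0.21 | −0.0768/0.5881 = −0.131 | −0.039 |
| 0.3 | −0.30 | −0.1152/0.6201 = −0.186 | −0.056 |

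Hand check at g = 0.2. The residual variance of Y12 is 0.36 × 0.64 × (1 − 0.21²) + 0.64 ≈ 0.860. The standard error of b is √(0.860/(0.588 × 368)) = 0.063, so z = −2.07, which is significant about 54% of the time. For the group-to-score path, z = 0.3/(2·√(0.588/368)) = 3.75, significant about 96% of the time. The product is about 52%.

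**Month-6 behavior added.** Y6 and Y0 together fix e6, so b = 0.

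**Raw change, no covariates.** M6 − M0 = 0.3·X − 0.4·M0 − g·e6 + u, so

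b = (−0.144·r0 − 0.384·g) / (0.16 + 0.64·g² + 0.5625)

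- r0 = 0: b = −0.053, −0.103, −0.148 for the three values of g.
- r0 = −0.3: b = +0.007, −0.045, −0.092. The baseline bias partly cancels the month-6 bias.
- r0 = −0.3 and g = 0: b = 0.0432/0.7225 = +0.060, which is bias from the missing baselines alone.

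**Simulated false mediation** (1,000 to 2,000 trials per scenario; where two figures appear, runs differed by a few points):

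| Model | g = 0.1 | g = 0.2 | g = 0.3 |
|---|---|---|---|
| Raw change, r0 = 0 | 11-14% | 34-37% | 61-65% |
| Raw change, r0 = −0.3 | 5% | 10% | 30% |
| Baselines added | 18% | 50-53% | 80-82% |
| Baselines and month-6 behavior | about 5% | about 5% | about 5% |

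A further run gave 5-63% for raw change, 16-83% with baselines only, and about 5% with month-6 behavior added. With g = 0 and r0 = 0 all three models give about 5%.

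**Real mediation** (score lowers later behavior by 0.2 per unit, g = 0). With r0 = 0 the raw-change slope is (0.048 − 0.1125)/0.7225 = −0.089 instead of −0.2. Detection is 25% with raw change, 82% with baselines, and 91% with month-6 behavior added.

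**Where there is no inflation.** In a second set of simulations (1,500 runs each, behavior correlation 0.5 or 0.7), if the drink moves neither the score nor month-6 behavior, every model declares mediation in about 5% of runs or fewer.

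**Form of the outcome.** In that set, with missing baselines and no path from month-6 behavior to the score, raw change gave false mediation in 10-21% of runs for the 12-month score as outcome and 25-29% for change from baseline.

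**The case against.** Two objections are strong, and both stand in part.

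**Silence is not exclusion.** Aim 3 lists no covariates for or against. The sentence that drops covariates concerns the primary analyses of Aims 1 and 2. A reader might infer that the plan rules out adjustment here, but the documents do not say so. The defect is an unspecified model, in which the baseline values and the form of the outcome are as open as month-6 behavior.

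**Adjusting for month-6 behavior can do harm.** A reader might conclude that the month-6-adjusted model is the correct one and should decide the claim. The documents do not support that. Score and behavior are scheduled at the same month-6 assessment, so their order is unknown. If score change has already acted on behavior by then, month-6 behavior lies on the causal path. In simulations where all real mediation runs that way, adjustment takes the indirect effect from −0.045, −0.053 or −0.064 to about zero. If a stable trait also drives behavior at every visit, adjustment can reverse the sign: a true −0.036 became +0.027 to +0.031, significant in 31-40% of runs. Random effects are among the covariance structures that Aims 1 and 2 will consider, so such a trait is not far-fetched.

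The pilot offers some reassurance, since "the omega-3 adolescent groups are similar at baseline and 6 months, and separate at 12 months". But that is a pattern of group means, and Aim 3 expects effects "by" month 12, which leaves room for earlier action.

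**Conclusion.** The point holds as a gap in specification with a real consequence. Run with no covariates, the 3b analysis can report mediation that is not there and can miss mediation that is. Adding only baselines, the obvious repair, restores power but leaves the month-6 problem: 16-83% false mediation in these scenarios, against about 5% with month-6 behavior added.

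Those figures rest on an assumed drink effect on the score (0.3), behavior correlation between visits (0.6), month-6 partial correlations (−0.11 to −0.30) and baseline correlation. The documents give none of these. The simulations also used a Monte Carlo interval or a joint test of the two paths in place of the bias-corrected bootstrap.

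A reader might infer that 3b will be declared whenever the drink raises a score. That goes too far: with weak confounding, or with a baseline correlation that offsets it, the raw-change rate is near 5%, and with no effect on the score or on month-6 behavior there is no inflation.

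This is a secondary hypothesis. The primary randomized comparisons are unaffected. Label: cheap improvement.

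**What to change.** Add to Statistical Methods, Aim 3:

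> The mediation regressions will include baseline score and baseline externalizing (same form and rater). The 12-month outcome regression will be reported both without and with 6-month externalizing. Mediation with the order cognition first, behavior later will be described as supported only if the two models agree. If they differ, the result will be reported as unable to separate mediation acting by month 6 from confounding by month-6 behavior.

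State also whether the outcome is the 12-month score or its change from baseline. Do not make the month-6-adjusted model the sole gate.

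**Cost.** Wording only, since all the data are already to be collected. The downside to name in the text is that, if score change acts on behavior by month 6, the adjusted model removes that real effect and may bias it, even to the opposite sign. Some true mediation will then be reported as unresolved.
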